2.3 Study Design	
This proposal uses a prospective cohort of CDI patients, 60 years of age and older, admitted to 2 sites of 1 Medical Center, and receiving “other” antibiotics, within 14-90 days of their CDI diagnosis.
 
These patients will be identified by a bioinformatics approach, using Clinical Looking Glass software developed at our medical center. All inpatients 60 years old or above, with a CDI laboratory diagnosis within 14-90 days of the present date will be assessed for use of antibiotics at high-risk for inducing CDI, as well as any concurrent C. difficile active antibiotics (“prophylaxis”). In addition, all new admissions to our hospital with a CDI diagnosis within 12 months are flagged for infection control purposes, and these patients will also be assessed for qualification into the study. Inclusion criteria are :
 
 1. CDI within 90 days 2. Use of high-risk antibiotics for inducing CDI within 72 hrs. of enrolment 3. No use of CDI active antibiotics within 24 hrs. 4. Able to sign consent for the study, or have an identified surrogate. 
As this is a pragmatic study, reflecting mostly standard medical care, there are few exclusion criteria :
 
 1. Prior CDI episode was felt to be colonization after chart review; 2. Subject not expected to survive 8 weeks (based on PI impression or chart review, considering factors including end-stage cancer, CHF, sepsis with high pressor requirement); 3. Documentation of current diarrhea (3 or more unformed stools per day) at time of enrollment, possibly due to CDI. 4. Receipt of prior fecal microbiota transplant or prior bezlotoxumab. 5. Congestive heart failure, as this diagnosis demonstrated increased mortality in the

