	
MODIFY studies with bezlotoxumab vs. placebo (Zinplava Package insert).
 
Those patients meeting the study inclusion/exclusion criteria will be offered open-label Bezlotoxumab infusion. This active intervention arm will have baseline stool samples collected for C difficile culture and typing at study entry and upon CDI relapse, if any
 
The comparator groups will be
 
 1. The historical control group from the Wong study, and 2. A concurrent observational arm – consisting of those patients otherwise eligible for the study, but : 
 A. Not consenting to study enrolment, and B. Taking no form of CDI prophylaxis (no oral vancomycin, metronidazole or fidaxomicin use as defined below). 
All cohort members will be subject to standardized chart review for baseline parameters at study entry, and structured followup by chart review every 2 weeks for 8 weeks for CDI relapse (the primary endpoint), tolerability of study drug (if administered) , length of hospitalization/ICU stay or death.
 
Use of CDI prophylaxis will be adjudicated to see if it conforms to the standards established in the Wong study – prophylaxis used for at least 50% of the duration of the concomitant antibiotics course and at least up to 72 hrs before the end of the concomitant antibiotics. Patients receiving any such prophylaxis will be excluded from the per-protocol analysis, which will be the primary analysis. Secondary analysis will also be performed on an intent-to-treat basis, where group assignment is determined based on use of prophylaxis at study entry only.
 
This design was chosen to parallel that of the retrospective Wong study at our same site – to allow comparisons with the historical treatment groups in that study.

2.4 Study Flowchart
	<pre> graph TD Cdiff_dx[14-90 days Cdiff dx] --> Inpatient Inpatient --> On_Abx{On Abx?} On_Abx -- No --> Follow_daily[Follow daily] On_Abx -- Yes --> On_CDI_ppx{On CDI ppx?} On_CDI_ppx -- Yes --> Offer_Bezlo[Offer Bezlo Study] Offer_Bezlo --> Enrol[Enrol] Offer_Bezlo --> Cdiff_Cx[C diff Cx and f/u 8 wks] On_CDI_ppx -- No --> Decline[Decline] Decline --> Follow_8_wk[Follow for 8 wk] Follow_8_wk --> Relapse_no_ppx[Relapse, no ppx No Relapse, no ppx] Follow_8_wk --> Relapse_Bezlo[Relapse, Bezlo No Relapse, Bezlo] </pre>

2.5 Study
	
STUDY DESIGN

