Procedures	
This prospective cohort study will be conducted using inpatients at the 1044 adult medical/surgical-beds on 2 campuses of the Montefiore Medical Center in the Bronx, New York. No work on this study will proceed until it is approved by our local Institutional Review Board.
 
SUBJECT IDENTIFICATION –INCLUSION CRITERIA
 
All patients with a laboratory diagnosis of CDI initially diagnosed within 3 months of screening, who are getting an order placed for inpatient antibiotics will be identified by bioinformatics—and will be eligible for study entry. They will be screened for concurrent use of metronidazole, oral vancomycin or fidaxomicin –if present; they will be rescreened for inclusion if further antibiotics are given without concurrent prophylaxis. If no prophylaxis is identified, then their providers will be approached to consider enrolling the patient into the current active arm for open-label Bezlotoxumab.
 
Inclusion criteria are :
 
 1. CDI within 90 days 2. Use of high-risk antibiotics for inducing CDI within 72 hrs of enrolment 3. No use of CDI active antibiotics within 24 hrs 4. Able to sign consent for the study, or have an identified surrogate. 
EXCLUSION CRITERIA
 
As this is a pragmatic study, reflecting mostly standard medical care, there are few exclusion criteria :
 
 1. Prior CDI episode was felt to be colonization after chart review(any physician-identified diarrhea is allowed, but not testing of asymptomatic patients such as test-of-cure testing or admission screening); 2. Subject not expected to survive 8 weeks; 3. Documentation of current diarrhea (3 or more unformed stools per day) at time of enrollment, possibly due to CDI. 4. Receipt of prior fecal microbiota transplant since the last CDI episode, or planned at time of screening or prior bezlotoxumab. 5. Congestive heart failure, as this diagnosis demonstrated increased mortality in the MODIFY studies with bezlotoxumab vs. placebo (Zinplava Package insert). 
CLINICAL DATA COLLECTION
 
Data on included patients will be collected by medical record review both manually and by using Clinical Looking Glass (CLG) software. Clinical data collected consists of patient demographics, comorbidities by ICD10 codes, length of hospital stay, nursing home residence, all antimicrobial agents received, use of proton pump inhibitors or histamine-2 blockers, all prior C. difficile assays, and severity of CDI markers on the date of CDI diagnosis – maximum temperature, maximum WBC, maximum creatinine, serum albumin –in order to calculate a Zar severity score (Zar, 2007). Manual chart reviews will be performed of all antibiotic courses for 8 weeks from enrollment and to assess for signs of CDI relapse, including symptoms such as abdominal pain or diarrhea as well as physical findings, vital signs, white blood cell, microbiologic data including both positive and negative C. difficile assays, and radiographic data. Particular weight will be given to assessment by infectious disease specialists, if consultation is performed.
 
DEFINITIONS
 
A valid high risk antibiotic course is defined as:
 
 1. Consisting of a beta lactam, carbapenem, quinolone, clindamycin, macrolide, or polymyxin, AND 2. Starting as early as 14days after the index CDI date, avoiding courses that

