--	---

	 L A A B B C C D D E E F F G G H H H L	
2.6 Study Duration	
Estimate of 1 year required to recruit 50 patients (from an estimated 150 eligible) and another 6 months to complete the study analysis. A computer simulation indicates there should be 150 eligible subjects in 1 year. Of these, ~50 will be on prophylaxis and ~50 will decline participation and will be followed as no prophylaxis controls.
	
2.7 Statistical Analysis and Sample Size Justification	
The PI and local statistician will be responsible for analyzing the study data.
 
Variables/Time Points of Interest
 
The primary outcome variable is relapse of CDI within 8 weeks of study entry. Secondary outcomes are relapse of CDI within 4 weeks of study entry (the interval with highest protective antibody levels), all-cause mortality, time to relapse and duration of hospitalization.
 
Baseline variables collected for each subject include : age, gender, number/dates/treatment of prior CDI episodes, current PPI use and H2-blocker use, Charlson score, immunosuppression, Inflammatory Bowel Disease or Irritable Bowel Syndrome, use of cathartics/lactulose, and indication for current antibiotics.
 
Variables related to the past CDI episode include markers of disease severity : WBC, fever >100.5°F, creatinine, albumin – to generate a Zar score (Zar,2007)
 
Statistical Methods
 
The analysis population is the per-protocol population, with 2 major comparator groups – those receiving Bezlotoxumab and those with no prophylaxis. The latter will be comprised of 3 subgroups – the control group from the Wong study and 2 concurrent observation groups- a PASSIVE followup group of subjects undergoing chart review , and an ACTIVE followup group of subjects declining study drug but agreeing to phone followup at 8 weeks. All groups will be compared across baseline parameters cited above. Risk factors pre-specified for recurrent CDI include age, immunocompromise, and severe CDI will be compared across groups, and tested for associations for the major outcomes of CDI relapse and mortality at 4 weeks and 8 weeks.
 
In the Wong study, there was a remarkably equal distribution of variables among the
	

[figure not shown]

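### The plan does not say that the heart-failure and 8-week-survival exclusions apply to the historical controls, so lower mortality on bezlotoxumab against a comparator that includes them could come from selection alone

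*Combined protocol and SAP*

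**What the plan says.** **Comparator.** Section 2.3 names two comparators: the historical no-prophylaxis group from the centre's earlier retrospective study of antibiotic prophylaxis, and a concurrent observational arm. Section 2.7 (Statistical Methods) sets bezlotoxumab against no prophylaxis and says of the second group: "The latter will be comprised of 3 subgroups". One of these is the historical group; the other two are concurrent. Section 2.7 (Power/Sample Size) also allows the control numbers to be raised by retrospective chart review or by merging in the historical arm.

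**Exclusions.** Sections 2.3 and 2.5 list, among others, "Subject not expected to survive 8 weeks" and "Congestive heart failure, as this diagnosis demonstrated increased mortality in the MODIFY studies with bezlotoxumab vs. placebo". Section 2.3 says the first is judged from the PI's impression or the chart, with end-stage cancer, heart failure and severe sepsis among the factors.

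**Who must pass them.** Treated patients must. So must the concurrent arm, described in section 2.3 as "consisting of those patients otherwise eligible for the study, but" not consenting and taking no prophylaxis. For the historical group, section 2.7 describes one restriction: 86 of the 144 unprophylaxed patients were aged 60 or over, and 23 of them relapsed.

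**Mortality.** Section 2.7 lists all-cause mortality as a secondary outcome. A later sentence says that pre-specified risk factors will be compared across groups and "tested for associations for the major outcomes of CDI relapse and mortality at 4 weeks and 8 weeks".

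**The concern.** Both exclusions remove patients at raised risk of death. If they shape the treated arm and the concurrent controls but not the historical controls, the historical group contains a high-mortality stratum that the treated arm lacks by design. Its mortality would then be higher even if bezlotoxumab had no effect on death.

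This matters because the protocol itself cites increased mortality with the drug in one subgroup. A comparator with inflated mortality could suggest a survival benefit, or make an unfavourable difference harder to see.

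For relapse, the primary outcome, the mismatch means that the historical rate of 26.7% may not describe patients who could have entered this trial. The sample size rests on that rate.

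**Working it through.** **1. Is any step stated that aligns the historical controls with the exclusions?**

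| Group | Age 60+ | Heart failure excluded | Not expected to survive 8 weeks excluded |
|---|---|---|---|
| Bezlotoxumab | yes | yes | yes |
| Concurrent controls | yes | yes (must be otherwise eligible) | yes (same reason) |
| Historical controls | yes (86 of 144) | not stated | not stated |

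The two blank criteria differ in strength. The heart-failure exclusion is justified only by bezlotoxumab data, which the reference list (2.11) dates to 2016-2017. The historical study was presented in September 2015 and concerned antibiotic prophylaxis, so it had no stated reason to use that criterion. The survival criterion has no drug-specific rationale, and the earlier study may or may not have used it.

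**2. The plan's own figures.** 23/86 = 26.7%, as stated. With p0 = 0.267 treated as a fixed known rate, n = [(1.960·√(p0(1−p0)) + 0.842·√(p1(1−p1)))/(p0−p1)]² gives 62.1 at p1 = 0.122 and 103.4 at p1 = 0.152. These match the stated 62 and 103. The sample size therefore depends entirely on the age-filtered historical rate.

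**3. Mortality from selection alone.** The documents give no mortality or heart-failure rates, so these inputs are assumptions: 8-week mortality of 10% in trial-eligible patients, 20% with heart failure and 60% in those not expected to survive. A share s = 5-10% of historical controls is not expected to survive, and a share c = 15-30% of the remainder has heart failure. The drug has no effect on death.

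Historical mortality: m = 0.60s + (1−s)[0.10(1−c) + 0.20c].
Pooled with 50 concurrent controls at 10%: (86m + 50 × 0.10)/136.
Spurious relative reduction: 1 − 0.10/(control mortality).

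| s | c | Historical m | Reduction | Pooled | Reduction |
|---|---|---|---|---|---|
| 5% | 15% | 13.9% | 28% | 12.5% | 20% |
| 5% | 30% | 15.3% | 35% | 13.4% | 25% |
| 10% | 15% | 16.4% | 39% | 14.0% | 29% |
| 10% | 30% | 17.7% | 44% | 14.9% | 33% |

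With 50 bezlotoxumab patients and a two-sided Fisher's exact test at 0.05, the chance of a significant result favouring bezlotoxumab is about 6-17% against the 86 historical controls and about 4-10% against the pooled 136. If the groups had equal mortality of 10%, it would be about 1.2% and 1.5%.

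**4. Relapse.** Suppose a share f = 10-40% of the 86 would have been excluded and relapsed at k = 0.5 to 2 times the rate of the rest (again assumptions). The rate in the eligible remainder is 0.267/(1 − f + fk). At f = 40% this is 0.267/0.8 = 33.4% for k = 0.5 and 0.267/1.4 = 19.1% for k = 2. The interval contains 26.7%, so the bias could go either way. Early deaths also shorten the time at risk of relapse.

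**The case against.** **The criteria are unknown, not known to differ.** A reader might infer that the exclusions were definitely not applied to the historical controls. The documents do not support that. They never give the earlier study's criteria, say the present design was chosen to parallel it, and call it similar or nearly identical. This stands as a limit on the wording. It does not close the gap, because similarity of design is not a statement about these two exclusions.

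**No mortality test against historical controls is written out.** The sentence containing "tested for associations for the major outcomes of CDI relapse and mortality at 4 weeks and 8 weeks" concerns risk factors, not treatment, and nothing says that historical mortality data exist. That is correct. The comparison follows from combining the three-part comparator with the list of secondary outcomes. The plan does not limit mortality to concurrent controls.

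**Safeguards exist.** Groups are compared at baseline, including Charlson score; comorbidities are collected by ICD10 code; a Cox model adjusts for covariates. These would help reveal a difference. But the Cox covariates are not listed, the model appears in the time-to-relapse paragraph where deaths are censored, and adjustment cannot repair a stratum that is absent from the treated arm. The interim check on self-selection concerns the current study and observation groups.

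**Harm would not be missed.** A reader might infer that safety monitoring depends on this comparison. It does not: heart-failure patients are not treated, and section 2.9 provides an independent Safety Officer who reviews serious adverse events after 12 and 25 subjects. What is at risk is the interpretation of the mortality result.

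**Relapse is biased in favour of the drug.** This too might be inferred, but step 4 of the working shows that the direction is undetermined.

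**Conclusion.** The concern holds as a gap in the plan. The comparator may include historical controls for whom only an age limit is described, while the treated arm and the concurrent controls must pass two exclusions related to the risk of death. If the plan is followed as written, a mortality comparison that includes these controls would probably favour bezlotoxumab. The inference is strong for heart failure and weaker for expected survival.

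The size, about 28-44% against historical controls alone and about 20-33% against the pooled comparator, is illustrative. It rests on assumed mortality rates and assumed shares of excludable patients. If the historical study did apply both exclusions, this bias disappears. For relapse, the supportable statement is only that the populations may differ. The concurrent controls are not affected by this mismatch.

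**What to change.** In section 2.7:

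1. Base the mortality comparison on bezlotoxumab versus concurrent controls.
2. State that before any historical or other retrospective patient enters the relapse comparator, the trial's exclusions will be applied by chart or ICD-code review, using only records dated up to the start of the qualifying antibiotic course. For expected survival this date limit is essential, because a judgement made with knowledge of later death would bias the group the other way.
3. Report results against historical and concurrent controls separately, with the number of historical patients removed by each exclusion.

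Sections 2.3 and 2.5 word the fecal-transplant exclusion differently and need to be reconciled before it is coded.

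**Cost.** A few sentences in the plan and a review of 86 records at the same centre, where chart and ICD-code review is already planned. Fewer than 86 historical controls may remain: under the assumptions in the working, 86(1−s)(1−c) is about 54 to 69. The mortality estimate will be less precise with about 50 concurrent controls, and self-selection among decliners remains.

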antibiotic prophylaxis and no prophylaxis groups. We similarly expect no imbalance between our current study and observation groups in terms of risk factor distribution, though self-selection bias will be considered at the interim analysis after 30 intervention patients are enrolled.

Categorical variables will be compared using chi-square and Fisher's Exact analysis and continuous variables will be compared using Mann-Whitney analysis, with $p < 0.05$ considered to be significant.

In survival analysis (Kaplan-Meier), time to CDI relapse is defined from the date of bezlotoxumab study dosing or study refusal - to the date of relapse and limited by a maximum observable window of 8 weeks from the dose of bezlotoxumab. Subjects are censored on the date of death, if death occurred within the observable window, or at the beginning of a new potential antibiotic prophylaxis course (i.e.. If within the 8 week observation period there is receipt of metronidazole, oral vancomycin or fidaxomicin.) or receipt of fecal microbiota transplant. A Cox proportional hazards model will be used for group comparison when adjusting for covariates.

The survival analysis from the Wong study, demonstrating the benefits of antibiotic prophylaxis on preventing relapsed CDI, is summarized in the following figure:

Relapse Free Duration

For the second objective, rates of CDI relapse will be compared among study subjects with or without *C. difficile* colonization at study entry. This is an exploratory study to inform future studies. It is expected that 20% of subjects will be colonized at study entry (based on Sunkesula, 2013) –the expected number of these that relapse is unknown, as data is conflicting on whether colonization is protective or predictive of relapse.

Power/Sample Size:

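### The plan names risk factors and a Cox model but ties neither to an adjusted estimate of the 8-week primary endpoint, although treatment follows consent and the concurrent controls declined it

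*Combined protocol and SAP*

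**What the plan says.** Section 2.7 (Variables/Time Points of Interest) states: "The primary outcome variable is relapse of CDI within 8 weeks of study entry". The secondary outcomes are 4-week relapse and "all-cause mortality, time to relapse and duration of hospitalization".

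For analysis, Section 2.7 (Statistical Methods) says: "Categorical variables will be compared using chi-square and Fisher's Exact analysis", with significance at p<0.05. Adjustment appears in one sentence, a Cox model that closes the time-to-relapse paragraph. It covers the same 8-week window and lists no covariates. Of baseline factors the section says "All groups will be compared across baseline parameters cited above", and then "Risk factors pre-specified for recurrent CDI include age, immunocompromise, and severe CDI will be compared across groups, and tested for associations" with relapse and mortality at 4 and 8 weeks.

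Treatment is open label and offered to eligible patients (Section 2.3). About 50 patients "will decline participation and will be followed as no prophylaxis controls" (Section 2.6). Of the no-prophylaxis comparator, Section 2.7 says "The latter will be comprised of 3 subgroups": the historical controls, and two concurrent groups followed by chart review or by telephone.

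On selection, the plan notes that the groups in the institution's earlier retrospective study were well balanced, and expects "no imbalance between our current study and observation groups in terms of risk factor distribution, though self-selection bias will be considered at the interim" analysis.

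**The concern.** Who receives the drug is decided by consent, so treated and concurrent control patients may differ in relapse risk for reasons unrelated to the drug. If higher-risk patients tend to decline, a crude comparison shows benefit that is not there. If higher-risk patients tend to accept, it hides benefit that is.

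The plan's reassurance comes from another contrast. The earlier study compared patients given antibiotic prophylaxis with patients given none, in retrospect. That says little about patients who accept a study infusion and patients who refuse it.

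Because no adjusted estimate is designated, two choices stay open until the data are seen: whether the crude or the adjusted result leads, and which of the many listed baseline variables enter the model. The study is a pilot, but Section 2.7 (Power/Sample Size) allows an extension to gain power and lets a strong effect prompt a placebo-controlled trial. Both decisions would draw on this estimate.

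**Working it through.** **The plan's own sizing.** Inputs from Section 2.7 (Power/Sample Size): control relapse 26.7% (23/86), treated relapse 12.2% or 15.2%, 80% power, two-sided 5%. The stated 62 and 103 reproduce as a comparison with a fixed control rate:

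n = [(1.960·√(p0(1−p0)) + 0.842·√(p1(1−p1))) / (p0−p1)]²

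- p1 = 0.122: [(0.867 + 0.275)/0.145]² = 62.1
- p1 = 0.152: [(0.867 + 0.302)/0.115]² = 103.4

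The sizing is therefore unadjusted as well.

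**Size of the confounding (illustration).** The documents do not say how consenters and decliners differ, so the strata and shares below are assumed. The drug has no effect. Two equally common strata relapse at 40% and 13.4% (mean 26.7%, ratio about 3). A 60/40 imbalance means that 60% of decliners and 40% of consenters are high risk.

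- Decliners: 0.6×0.40 + 0.4×0.134 = 29.36%
- Consenters: 0.4×0.40 + 0.6×0.134 = 24.04%
- Spurious difference: 5.3 points
- Pooled comparator (50 decliners plus the 86 historical controls aged 60 or over, at 26.7%): (50×0.2936 + 86×0.267)/136 = 27.68%, a difference of 3.6 points

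False-positive rates come from exact enumeration at two-sided p<0.05, chi-square without continuity correction. For the pooled case the control count is the sum of the two binomials.

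| Assumed imbalance | 50 v 50: points, chi-square (Fisher) | 50 v 136 pooled: points, chi-square (Fisher) |
|---|---|---|
| none | 0; 5.1% (3.1%) | 0; 5.1% (4.1%) |
| 55/45 | 2.7; 6.1% (3.8%) | 1.8; 5.5% (4.4%) |
| 60/40 | 5.3; 9.3% (6.2%) | 3.6; 7.3% (6.1%) |
| 65/35 | 8.0; 14.7% (10.4%) | 5.5; 10.7% (9.1%) |
| 60/40, milder gradient (36.8% and 16.6%) | 4.0; 7.5% (4.8%) | 2.8; 6.2% (5.1%) |

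**Opposite direction.** Suppose the drug works and consenters are the higher-risk group, 60% v 40% on each of three assumed factors. Pooled crude power then falls from 57% to about 40% (12.2% relapse) and from 37% to about 23% (15.2%).

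**Can the data carry adjustment?** Expected relapses:

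- 50 v 50: 50×0.267 + 50×0.122 = 19.5, or 21.0 at 15.2%
- 50 v 136: 136×0.267 + 50×0.122 = 42.4, or 43.9 at 15.2%

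Treatment plus three covariates is four parameters: about 5 relapses per parameter in the prospective cohort and about 11 when pooled.

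**What adjustment does.** Simulation with three measured binary confounders (assumed odds ratio 1.59 each), Firth logistic regression standardised to a risk difference, 20,000 null trials per scenario:

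- 50 v 50: bias falls from 5.3 to 0.0 points (60/40) and from 8.0 to 0.1 (65/35). The standard error rises by 1% and 7%. False positives are 4.9% and 5.1%.
- Pooled, with covariates known for all: bias falls from 3.7 to 0.2 and from 5.4 to 0.3 points. The standard error rises by 2% and 6%.
- One of the three confounders unmeasured (60/40): 1.8 of 5.3 points remain at 50 v 50, and 0.9 of 3.6 pooled.

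A separate run of 3,000 trials agreed: bias 5.4 to 0.1 and 7.8 to 0.1 points at 50 v 50, standard error 0% to 9% larger, false positives 4.6% to 5.5%.

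**The case against.** The strongest reply is that the plan already foresees adjustment. Its Cox model has the same event and the same 8-week window as the primary endpoint, three risk factors are called pre-specified, and self-selection is named as an interim topic. Reading those factors as the Cox covariates is natural. This stands in part. A reader might infer that the plan ignores confounding or offers no adjusted analysis, and the documents do not support that. What they lack is the link: the factors are assigned only to group comparisons and association tests, and the Cox model serves a secondary outcome.

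Second, every figure for size is assumed. Eligibility already narrows the risk mix (age 60 or over, recent infection, high-risk antibiotics, heart failure excluded), and on the pooled comparator inflation is modest unless imbalance is strong. This stands. Narrower eligibility does not, however, show that consenters and decliners are alike.

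Third, near-zero residual bias is optimistic, because the simulation fits the covariates that generated the data. The documents do not confirm that the historical controls have them. Section 2.7 (Power/Sample Size) also says relapse information was less complete in the earlier study. No covariate removes that difference. This stands and shapes the fix.

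Fourth, the study is a pilot, and a later placebo-controlled trial would resolve the confounding. This limits the stakes but does not remove them. How deaths and later CDI-active antibiotics count in the binary endpoint is a separate question that faces the crude test equally.

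**Conclusion.** The concern holds. The only method stated that fits the binary primary endpoint is unadjusted, treatment follows consent, and the factors the plan calls pre-specified are not tied to any estimate of the treatment effect. This should be corrected, but it does not invalidate the study.

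The size is conditional. Under no drug effect and a threefold gradient, the 60/40 case roughly doubles the nominal 5% chi-square error at 50 v 50 and raises it modestly when pooled. The 55/45 case hardly matters. A reader might infer that the trial will show a false benefit, or that decliners are the sicker group. The documents give no information on how the two groups differ, so neither the direction nor the amount of bias is known. The 14.7% figure in particular needs a 65/35 split, the threefold gradient, chi-square rather than Fisher, and no historical controls.

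**What to change.** Before outcomes in the prospective cohort are examined, amend Section 2.7 as follows.

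- Designate one covariate-adjusted 8-week estimate with 95% CI as primary. Penalised logistic regression standardised to a risk difference is one suitable choice among several.
- Fix the covariates as exactly the three factors already named: age, immunosuppression and severity of the index infection. Allow no additions that depend on the data, including at the interim.
- Use the same list in the Cox model, and keep chi-square/Fisher as supportive.
- Keep the comparator as defined, but confirm in advance that the three covariates exist for the historical controls. If one does not, fix the reduced pooled list before outcomes are seen.
- Show the concurrent-only adjusted result alongside, because adjustment cannot remove the period difference in relapse ascertainment.
- State that unmeasured reasons for refusal remain.

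The cost is analysis text and a little programming. No controls are given up, and the variables are already to be collected for the prospective cohort. The standard error is about 0% to 9% larger. Penalisation shrinks a true 14.5-point effect to about 13.6. In balanced groups at 50 v 50, power is 44% adjusted against 46% crude (12.2% relapse) and 30% against 31% (15.2%, simulated). With about five relapses per parameter in the prospective cohort, the list must stay at three.

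### Deaths are censored in the Kaplan-Meier analysis, so 1-KM overstates 8-week relapse, and no rule covers deaths in the primary outcome or hospital stay

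*Combined protocol and SAP*

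**What the plan says.** All of the relevant text is in section 2.7 of the combined protocol and SAP.

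- **Primary outcome** (Variables/Time Points of Interest): "The primary outcome variable is relapse of CDI within 8 weeks of study entry".
- **Secondary outcomes** (same heading): relapse within 4 weeks, followed by "all-cause mortality, time to relapse and duration of hospitalization".
- **Tests** (Statistical Methods): "Categorical variables will be compared using chi-square and Fisher's Exact analysis", and "continuous variables will be compared using Mann-Whitney analysis". The first covers the binary primary outcome and the second covers hospital stay.
- **Time to relapse** (Statistical Methods): "Subjects are censored on the date of death, if death occurred within the observable window". Follow-up is also censored "or at the beginning of a new potential antibiotic prophylaxis course" or at fecal microbiota transplant. For adjustment, "A Cox proportional hazards model will be used for group comparison when adjusting for covariates".
- **Mortality**: besides being a secondary outcome, it appears where pre-specified risk factors are "tested for associations for the major outcomes of CDI relapse and mortality at 4 weeks and 8 weeks".

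The documents do not say how a patient who dies before week 8 without relapse enters the chi-square or Fisher test. They do not say how an in-hospital death enters the comparison of stay. No competing-risk method is named.

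**The concern.** Kaplan-Meier with deaths censored estimates relapse as if the patients who died were still at risk and would relapse at the same rate as the survivors. In a hospitalized population aged 60 and over, death is a real alternative outcome. The curve then answers a hypothetical question, and 1-KM at week 8 exceeds the share of patients who actually relapse. A clinician reading it as absolute risk would be misled.

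The second gap is silence. A binary outcome forces a choice for each death without relapse: score it as no relapse, exclude it, or treat it as missing. Stay has the same problem, because an early in-hospital death entered at its face value ranks as a short stay, which reads as favourable. With open-label treatment and about 50 patients per group, these choices should not be left until the data are in.

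The gap matters most if mortality differs between groups. That is possible here because the comparison is not randomised: consenting patients are set against decliners and against historical controls. The plan itself foresees self-selection.

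**Working it through.** **Inputs from section 2.7 (Power/Sample Size).** Control relapse is 23/86 = 26.7%, which reproduces the plan's figure as a simple proportion. Expected relapse on bezlotoxumab is 12.2% to 15.2%. Expected enrolment is 50 and 50.

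**Assumptions.** The documents give no mortality figure, so 8-week mortality *d* is set at 10% and 20%. Hazards are constant over 8 weeks, and there is no other censoring.

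**Step 1. How far 1-KM exceeds actual relapse.** The answer depends on what 26.7% means.

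*Crude reading:* 26.7% is the share who actually relapse and *d* is the share who die first. With T = 0.267 + d, the relapse hazard is h = −ln(1 − T) × 0.267/T, and 1-KM = 1 − exp(−h).
- d = 10%: T = 0.367, h = 0.4573 × 0.267/0.367 = 0.3327, 1-KM = 28.3%
- d = 20%: T = 0.467, h = 0.6292 × 0.267/0.467 = 0.3598, 1-KM = 30.2%

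*Net reading:* 26.7% and *d* are the risks with the other event absent. Then λr = −ln(0.733) = 0.3106, λd = −ln(1 − d), and cumulative incidence (CIF) = λr/(λr + λd) × [1 − exp(−(λr + λd))].
- d = 10%: λd = 0.1054, CIF = 0.3106/0.4160 × 0.3403 = 25.4%
- d = 20%: λd = 0.2231, CIF = 0.3106/0.5338 × 0.4136 = 24.1%

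| Assumed mortality | Crude: actual → 1-KM | Excess | Net: actual → 1-KM | Excess |
|---|---|---|---|---|
| 10% | 26.7% → 28.3% | 1.6 | 25.4% → 26.7% | 1.3 |
| 20% | 26.7% → 30.2% | 3.5 | 24.1% → 26.7% | 2.6 |

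**Step 2. Relative effect under equal mortality.** Applying the CIF formula to 26.7% and 12.2%, the risk ratio is 0.457 with no deaths and 0.455 to 0.457 for mortality of 5% to 30% in both groups. Absolute risks fall, but the ratio hardly changes.

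**Step 3. What the missing primary rule leaves open (net reading, control group).** If deaths without relapse count as no relapse, the proportion is the CIF. If they are excluded, it is CIF/(1 − share dying first).
- d = 10%: 25.4%, or 0.2541/(1 − 0.0862) = 27.8%
- d = 20%: 24.1%, or 0.2407/(1 − 0.1729) = 29.1%

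At 20% mortality the two rules differ by 5.0 points for the same patients.

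**Step 4. Unequal mortality, no true relapse effect, deaths counted as no relapse.** At 10% v 20% mortality the proportions are 25.4% v 24.1%. The 1.3-point gap is 0.65 of a patient in 50. Its standard error is √(0.254 × 0.746/50 + 0.241 × 0.759/50) = 8.6 points. The two-sided rejection rate is 5.3%, and at 10% v 30% it is 6.2%.

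**Step 5. Hospital stay, no true effect, deaths entered as short stays.** This was simulated with 3,000 runs and 50 per arm. Stay was assumed lognormal (median 10 days, log-SD 0.8), with death cutting the stay at a uniformly distributed point.

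| In-hospital deaths | Mann-Whitney rejection at 0.05 |
|---|---|
| 10% v 10% | 5.0% |
| 20% v 10% | 6.9% |
| 30% v 10% | 13.2% |

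Simulation error at 6.9% is √(0.069 × 0.931/3000) = 0.5 points. The bias favours the arm with more deaths.

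**The case against.** The strongest reply is that little of this affects the comparison. Censoring death in a Cox model is the standard way to estimate a cause-specific hazard ratio. Equal mortality leaves the risk ratio where it was, and mortality is reported separately. Patients not expected to survive 8 weeks are excluded. So are those with congestive heart failure, the subgroup in which the plan cites excess mortality with the drug. The study calls itself a pilot. All of this stands, and it limits the point to absolute risks, missing rules and the stay comparison. The exclusions reduce deaths, but they do not make mortality equal between self-selected groups.

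A reader might infer more than the documents support, in three ways.

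- *That the plan scores deaths as no relapse and as short stays.* These are plausible defaults, but neither is written. Section 2.5 (Definitions) also lets autopsy evidence of colitis support a relapse, so a death is not automatically a non-relapse.
- *That the primary proportion is biased in the opposite direction to the curve.* It is not. With complete 8-week follow-up, the proportion with deaths counted as no relapse is the cumulative incidence itself.
- *That cumulative incidence would remove the 1.3-point gap in Step 4.* It would not. The gap comes from the cumulative incidence formula, so an Aalen-Johansen curve shows it too. A cause-specific hazard ratio would show no effect there, which is why both are needed, alongside mortality.

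**Conclusion.** The point holds, with limited scope. Censoring deaths makes 1-KM overstate actual 8-week relapse by about 1.3 to 1.6 points at 10% mortality and 2.6 to 3.5 points at 20%. These figures rest on constant hazards and on assumed mortality. The planned Cox model is sound as a cause-specific analysis.

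For the primary outcome the defect is a missing rule. At 20% mortality it leaves a control rate of 24.1% or 29.1% open to later choice. For hospital stay the defect is also a missing rule. Its consequence is conditional: if deaths are entered as short stays and mortality differs, the false-positive rate rises to about 6.9% at 20% v 10%, under the assumed stay distribution. Material bias between groups needs unequal mortality. The documents neither show it nor rule it out, and its direction is unknown. This should be corrected before analysis, but it does not invalidate the design.

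**What to change.** In section 2.7:

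1. Present relapse at 4 and 8 weeks as Aalen-Johansen cumulative incidence with death without relapse as a competing event.
2. Keep the Cox model and label its result a cause-specific hazard ratio.
3. State how a death without relapse enters the chi-square or Fisher test. Counting it as no relapse matches the cumulative incidence. Add relapse or death within 8 weeks as a sensitivity analysis of the primary outcome.
4. Keep duration of hospitalization, but rank in-hospital deaths worst in the Mann-Whitney test, and report deaths beside it.

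The cost is a few sentences and a few lines of code, since section 2.3 already has death and length of stay reviewed every 2 weeks for 8 weeks. The documents do not say whether dates of death exist for the historical controls; if they do not, limit items 1 and 4 to the concurrent cohort.

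There is a small downside: the stay comparison is no longer plain length of stay, and higher mortality will now count against an arm. Replacing stay with days alive and out of hospital is not necessary, and would also require every readmission to be captured. Item 1 does not address the separate censoring at new CDI-active antibiotics or transplant, which still has to be justified as unrelated to relapse risk.
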